5 STUDY TREATMENT

5.1 Description of Investigational Drug

Active:

Code name: ORMD-0801

Dosage form: 2 soft gel capsules per dose

Strength: 230 IU insulin (8 mg insulin) per capsule

Description: API (recombinant human insulin USP), in Oramed's proprietary formulation [aprotinin, SBTI, disodium EDTA, fish oil, and TWEEN 80] in capsules.

Placebo control:

Fish oil in capsules, identical in appearance to ORMD-0801

Note: 230 IU Insulin and placebo capsules are all identical in appearance.

5.1.1 Packaging and Labeling

This study is a double-blind, double-dummy study. The Investigational Site pharmacist will be responsible for dispensing the appropriate treatment period study treatment based on the randomization schedule. For each treatment period dose, the pharmacist will remove the capsules from the bottle before providing the capsules to the Investigational Site personnel.

Shipments of placebo capsules for the run-in period will be clearly labeled to indicate they should be used during this patient-blinded stage of the study. Shipments of study medication for the double-blinded treatment period will be received in blinded packages so that the Investigator, staff, and patients will be blinded to the treatment. Study medication will be dispensed to the site with instructions for when treatment can be administered and with a diary for recording administration of study medication. Medication containers and any unused capsules will be retained at the study site after the treatment phase of the trial is complete.

The treatment packages will be labeled with the following information:

- Study number
- Patient ID
- Kit No./Bottle ID
- Dosage Form/Content
- Directions for use, including route of administration
- Number of capsules in package
- Storage conditions
- Instructions to "keep out of reach of children"
- Caution: New Drug – Limited by Federal (or United States) law to investigational use.
- Name of Sponsor

A separate label with the identical information will be provided with the label on the package for drug accountability purposes.

5.1.2 Storage and Handling

All study treatment must be kept in an appropriate, secure area to prevent unauthorized access. The study treatment is to be shipped under ambient conditions and stored in the original packaging at controlled room temperature (62 to 77°F; 17 to 25°C). Excursions between 59 to 86°F (15 to 30°C) will be permitted. Excessive humidity should be avoided. Storage conditions will be monitored and appropriate monitoring logs maintained as source data. Deviations from the established temperature, as well as the occurrence of excessive humidity, should be documented, and the Sponsor should be notified.

Study treatment should be handled and disposed of using proper procedures as defined by Investigational Site standard operating procedures (SOPs) for Investigational Drugs.

5.2 Randomization

This is a single center, randomized, double-blind, 3-way crossover study. Approximately 30 eligible subjects will be randomized to placebo and 2 of the 3 possible dose groups: ORMD-0801 460 IU qd (in the evening), ORMD-0801 460 IU bid (in the morning and evening) and ORMD-0801 460 IU tid (morning, afternoon, and evening).

In order to estimate the morning, afternoon, and evening PD effect, each subject will have one period in which the PD blood samples are drawn in the morning, one period in which the PD blood samples are drawn in the afternoon and one period in which the PD blood samples are drawn in the evening. When the subject is on active therapy, the PD blood samples will be drawn after an active therapy dose (not after the placebo dummy). Thus, if the subject is taking ORMD-0801 460 IU qd, the PD blood samples will be drawn in the evening. If the subject is taking ORMD-0801 460 IU bid, the PD blood samples will be drawn in the morning or evening. If the subject is taking ORMD-0801 460 IU tid or placebo, the PD blood samples will be drawn in the morning, afternoon, or evening.

Integrium, LLC will generate and implement the randomization procedures for this trial. A computer-generated randomization schedule will be used for assigning treatment (active or placebo). The Investigational Site pharmacist will follow this randomization schedule to dispense the appropriate study treatment.

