5.3.1.2 Double-Blind Treatment Administration

Study treatment (active or placebo) will be administered during Visit 2 on Days 4-8. **Prior to administering the scheduled dose of study drug, the most recent available reading on the CGM monitor must indicate a blood glucose of ≥ 70 mg/dL.** On all days, subjects will receive a dose of study treatment or placebo at approximately 7am (\pm 60 minutes), approximately 1pm (\pm 60 minutes), and a dose before bed at approximately 10 pm (\pm 60 minutes).

Subjects may be randomized to receive ORMD-0801 qd, bid, or tid:

- Subjects receiving ORMD-0801 qd will receive their dose at approximately 10pm (\pm 60 minutes), while receiving identical placebo at approximately 7am (\pm 60 minutes) and at approximately 1pm (\pm 60 minutes).
- Subjects receiving ORMD-0801 bid will receive their doses at approximately 7am (\pm 30 minutes) and before bed at approximately 10pm (\pm 60 minutes), while receiving placebo at approximately 1pm (\pm 60 minutes).
- Subjects receiving ORMD-0801 tid will receive their doses at approximately 7am (\pm 60 minutes), at approximately 1pm (\pm 60 minutes), and before bed at approximately 10pm (\pm 60 minutes).

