8.3 Continuous Glucose Monitor Evaluation

For the purpose of analysis:

- 24-hour will be considered to be from 6AM to 6AM,
- Daytime will be considered to be from 6AM to 10PM, and
- Nighttime will be considered to be from 10PM to 6AM.

The last 2 days with at least 80% of expected measurements prior to dosing will be considered the run-in days for each of the parameters. The last 2 days with at least 80% of expected measurements prior to 8 hours after the last dose will be considered the on treatment days. The measurements more than 8 hours after the last dose will be considered the follow-up days.

The area under the curve (AUC) will be derived for each of the time periods (24-hour, daytime and nighttime) using the indicated days (run-in days, treatment days and follow-up days). The average glucose measurement will be derived by dividing the AUC by the number of observed hours. The average change from run-in will be derived for each treatment regimen for both the treatment days and the follow-up days.

The placebo adjusted change in means will be derived for each of the active therapy regimens by subtracting the placebo mean (the mean change from run-in while the subject was receiving placebo) from the active therapy mean (the mean change from run-in while the subject was receiving the active therapy). The placebo adjusted change in means will be derived for both the treatment days and the follow-up days.

The placebo adjusted change in means will be analyzed using an Analysis of Variance (ANOVA) with treatment as the main effect to determine whether multiple doses a day has an effect on the CGM parameters.

The ratios of the placebo adjusted change in means between the active treatments within each subject will also be derived to estimate the magnitude of the dose response.

Summary statistics will be presented for both the placebo adjusted change in means and the ratios of the placebo adjusted change in means. Analysis results will be presented for the change in means.

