1.3.2 Secondary Objectives

Secondary objectives are:

- To compare pre-treatment (Day 3) to end of treatment (Day 8) mean daytime CGM glucose for single and multiple doses of ORMD-0801 vs placebo.
- To compare pre-treatment (Day 3) to end of treatment (Day 8) mean nighttime CGM glucose for single and multiple doses of ORMD-0801 vs placebo.
- To compare pre-treatment (Day 3) to post-treatment washout (Day 9) 24-hour CGM glucose for single and multiple doses of ORMD-0801 vs placebo.
- To compare post-prandial glucose measurements for single and multiple doses of ORMD-0801 vs placebo.

- To compare pre-treatment (Day 3) to end of treatment (Day 8) insulin pharmacokinetics (PK) for single and multiple doses of ORMD-0801 vs placebo.
- To compare pre-treatment (Day 3) to end of treatment (Day 8) C-peptide pharmacodynamics (PD) for single and multiple doses of ORMD-0801 vs placebo.
- To compare defined events of hypoglycemia for single and multiple doses of ORMD-0801 vs placebo.

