2.8. Efficacy Evaluations

2.8.1. Continuous Glucose Monitoring

The last 2 days with at least 80% of expected measurements prior to dosing will be considered the run-in days for each of the parameters. The last 2 days with at least 80% of expected measurements prior to 8 hours after the last dose will be considered the on treatment days. The measurements more than 8 hours after the last dose will be considered the follow-up days.

The 24-hr period (6AM to 6AM), nighttime (from 10pm to 6am), daytime (6AM to 10PM), and post-prandial (first hour after meal start time including breakfast, lunch, and dinner) glucose values will be summarized. The mean, standard deviation, minimum, maximum, first quartile, median, third quartile and inner-quartile range will be presented.

The area under the curve (AUC) will be derived for each of the time periods (24-hour, daytime and nighttime) using the indicated days (run-in days, treatment days and follow-up days). The average glucose measurement will be derived by dividing the AUC by the number of observed hours. The average change from run-in will be derived for each treatment regimen for both the treatment days and the follow-up days.

The placebo adjusted change in means will be derived for each of the active therapy regimens by subtracting the placebo mean (the mean change from run-in while the subject was receiving placebo) from the active therapy mean (the mean change from run-in while the subject was receiving the active therapy).

The placebo adjusted change in means will be derived for both the treatment days and the follow-up days. The placebo adjusted change in means will be analyzed using an Analysis of Variance (ANOVA) with treatment as the main effect to determine whether multiple doses a day has an effect on the CGM parameters. If the residuals are not normally distributed, then a Kruskal-Wallis test (one-way analysis of variance on the ranks) will be performed.

The ratios of the placebo adjusted change in means between the active treatments within each subject will also be derived to estimate the magnitude of the dose response.

Summary statistics will be presented for both the placebo adjusted change in means and the ratios of the placebo adjusted change in means. Analysis results will be presented for the change in means.

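### All regimens share the 10pm dose, yet no planned test compares nighttime ORMD-0801 with placebo; a pooled active-vs-placebo night contrast should be added

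*Protocol*

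**What the plan says.** Each subject takes placebo and two of the three active regimens: "Approximately 30 eligible subjects will be randomized to placebo and 2 of the 3 possible dose groups" (Protocol 5.2). The regimens are "qd (in the evening), ORMD-0801 460 IU bid (in the morning and evening) and ORMD-0801 460 IU tid (morning, afternoon, and evening". Protocol 5.3.1.2 fixes the clock times: "Subjects receiving ORMD-0801 qd will receive their dose at approximately 10pm", and the last dose of bid and tid is also at about 10pm. The regimens differ only at 7am (active in bid and tid) and at 1pm (active in tid).

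The analysis windows follow the clock. Protocol 8.3 states "Nighttime will be considered to be from 10PM to 6AM" and "Daytime will be considered to be from 6AM to 10PM"; SAP 2.8.1 repeats them.

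The secondary objective in SAP 1.3.2 concerns "mean nighttime CGM glucose for single and multiple doses of ORMD-0801 vs placebo". For the analysis, SAP 2.8.1 says: "The placebo adjusted change in means will be derived for each of the active therapy regimens". These values go into a one-way ANOVA with treatment as the main effect, whose stated purpose is to see whether multiple daily doses have an effect. Kruskal-Wallis is the fallback. No pooled active-versus-placebo contrast is specified for any CGM window.

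**The concern.** During the night window the three regimens have just delivered the same dose. Unless earlier doses carry over, they are three labels for one night treatment. The plan keeps them apart and then tests whether they differ.

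A placebo-adjusted change is already a difference from placebo, so an ANOVA across regimens asks whether qd, bid and tid depart from placebo by the same amount. If the shared dose lowers night glucose equally in all three, that null hypothesis is true however large the drug effect is. A clear nighttime effect could thus coexist with a non-significant planned test.

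The drug-versus-placebo comparison is left to three summaries of about 20 subjects each, although the design supplies 60 active and 30 placebo periods. Night glucose matters for this product: the Protocol introduction names lowering of fasting glucose as the initial indication and builds the regimens on bedtime dosing.

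**Working it through.** **Inputs.** 30 subjects and three periods each (Protocol 5.2). Assumption: 10 subjects per regimen pair, hence 20 per active regimen; the actual split is in a separate randomization plan (SAP 2.12). Let s² be the within-subject variance of one period's change from run-in. The documents give no SD, effect size, alpha or power, so there is no figure of the plan's to reproduce, and results are in units of s².

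**1. Planned regimen-specific estimate.** A placebo-adjusted change is the difference of two periods, with variance 2s². The mean of 20 has variance 2s²/20 = 0.100 s².

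**2. Pooled estimate.** Average each subject's two active periods and subtract the placebo period: variance s²/2 + s² = 1.5 s². Over 30 subjects, 1.5 s²/30 = 0.050 s².

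**3. Same model for both.** Least squares with subject and period terms, 10 subjects per pair with orders spread over the six permutations, gives:

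| Estimate vs placebo | Variance |
|---|---|
| Planned paired mean, one regimen | 0.100 s² |
| One regimen, subject and period model | 0.090-0.093 s² |
| All active pooled, same model | 0.0505 s² |

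Like for like, 0.090/0.0505 = 1.78 and 0.093/0.0505 = 1.84, so about 1.8. Against the planned mean, 0.100/0.0505 = 1.98. Part of the factor of 2 therefore comes from the model and not from pooling.

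**4. Sensitivity.** With 18 to 22 subjects per regimen, the ratio of the planned to the pooled variance (0.050 s²) runs from (2/22)/0.050 = 1.82 to (2/18)/0.050 = 2.22. If the drug effect also varies between subjects with variance t², the ratio is 1.5(2s² + t²)/(1.5s² + t²): 2.0 at t² = 0, 1.8 at t² = s², and 1.5 in the limit. Hence the range 1.5 to 2.2.

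**5. The planned F test.** Simulated with the same effect in all regimens, it rejects in just under 2% of trials at the nominal 5% level (1.8% in 20,000 trials with a common effect of 0.8 s). A common effect cancels from the comparison. The rate falls below 5% because a subject's two differences share one placebo period (correlation 0.5) and the ANOVA has no subject term.

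**6. A trap in pooling.** Treating the 60 placebo-adjusted differences as independent gives 2s²/60 = 0.033 s² instead of 0.050 s². The standard error would be too small by 1 − √(0.033/0.050), about 18%.

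**7. When pooling would mislead.** If only tid differed at night, by x·s, the pooled estimate would be off by x·s/3 as an estimate of the qd effect. Its mean squared error exceeds that of the planned qd mean when x²/9 > 0.100 − 0.050, that is x > 0.67 (x > 0.60 against the model-based 0.090 s²).

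**8. Daytime.** Bid and tid differ only from 1pm. An effect confined to 1PM-10PM covers 9 of the 16 daytime hours and appears in the 6AM-10PM mean multiplied by 9/16 = 0.56.

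**The case against.** The strongest reply is that regimen-specific estimates are what the objectives ask for, since they speak of single and multiple doses. Pooling answers whether any ORMD-0801 regimen affects the night, which is a different question, in a trial that SAP 2.11 says is not powered, on a secondary endpoint. This stands as a reason to keep the regimen-specific results. It does not supply a test against placebo, which the objective also names. SAP 2.1 allows 95% confidence intervals where appropriate, but SAP 2.8.1 does not list them for these changes, and they would again be per regimen.

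A second reply is that a common night effect is nowhere stated. The Protocol introduction describes a delayed onset of action, the Day 9 comparison leaves persistence open, and dosing is conditional on a CGM reading (Protocol 5.3.1.2), so 10pm doses actually taken could differ by regimen. The 8-hour rule in SAP 2.8.1 would place the end of a 1pm dose at 9pm, before the window opens, but it sorts readings into treatment and follow-up and is not given as a duration of action. This also stands: the variance gain is conditional.

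Three stronger readings do not hold:

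- That the plan uses twice the necessary variance. This presumes the common effect.
- That the plan loses power in three regimen-versus-placebo tests. It specifies no such tests.
- That the 16-hour daytime window is an error. Mean daytime glucose is the stated objective, the tid-versus-bid difference is unbiased for it, and post-prandial summaries for lunch and dinner already give some time-of-day information.

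**Conclusion.** The point holds as a gap and a conditional loss of efficiency. The gap is that no specified test addresses nighttime ORMD-0801 versus placebo; this follows from the text alone. The loss is that, if the night effect is similar across regimens, a pooled contrast cuts the variance by a factor of about 1.8 within the same model and about 2 against the planned paired mean (range 1.5 to 2.2). That rests on near-equal allocation to regimen pairs and on the similarity of nights, which the 8-hour rule is compatible with but does not establish. If daytime doses carry over, the pooled estimate becomes an average over regimens but remains a valid test of no drug effect. No stated figure is wrong and the primary endpoint is untouched. The daytime dilution is a matter for an optional summary only.

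**What to change.** In SAP 2.8.1 and Protocol 8.3:

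1. Beside the regimen-specific nighttime estimates, add a pooled all-active versus placebo contrast. Fit it to the period-level change from run-in in a mixed model with subject and period terms, not to the 60 placebo-adjusted differences taken as independent.
2. From the same model, report the qd, bid and tid night comparison as a check on whether the regimens differ. State that the pooled estimate is an average over regimens if they do.
3. Optionally, as a descriptive supportive summary, report the daytime change by dose interval, for example 7AM-1PM and 1PM-10PM. With doses allowed ±60 minutes around 1pm, these windows match the dose only approximately, and they leave out 6AM-7AM.

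Leave the 24-hour and daytime endpoints as they are. The cost is SAP wording and one further model on data already collected. It adds one contrast to a plan without multiplicity control, so the contrast should be labelled as belonging to the secondary nighttime objective.

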5.3 Study Treatment Administration

5.3.1 Study Treatment Periods

In order to achieve the desired 460 IU, 2 capsules will be administered per dose. Accordingly, subjects who are randomized to placebo will also receive 2 identical placebo capsules per dose.

5.3.1.1 Single-Blind Placebo Administration

Placebo will be administered during Visit 2 on Days 1, 2, 3, and 9. On Day 1, subjects will receive one dose of placebo in the morning, followed by breakfast at least 45 minutes later. They will receive 4 additional doses of placebo to take one dose at least 45 minutes before lunch, one dose at bedtime, one dose at least 45 minutes before breakfast on Day 2, and one dose at least 45 minutes before lunch on Day 2. Subjects will be provided with an evening dose of placebo at approximately 10 pm (\pm 60 minutes) on Day 2. On Days 3 and 9, subjects will receive a dose of

single-blind placebo at approximately 7am (\pm 60 minutes), approximately 1pm (\pm 60 minutes), and before bed at approximately 10 pm (\pm 60 minutes).

5.3.1.2 Double-Blind Treatment Administration

Study treatment (active or placebo) will be administered during Visit 2 on Days 4-8. **Prior to administering the scheduled dose of study drug, the most recent available reading on the CGM monitor must indicate a blood glucose of ≥ 70 mg/dL.** On all days, subjects will receive a dose of study treatment or placebo at approximately 7am (\pm 60 minutes), approximately 1pm (\pm 60 minutes), and a dose before bed at approximately 10 pm (\pm 60 minutes).

Subjects may be randomized to receive ORMD-0801 qd, bid, or tid:

- Subjects receiving ORMD-0801 qd will receive their dose at approximately 10pm (\pm 60 minutes), while receiving identical placebo at approximately 7am (\pm 60 minutes) and at approximately 1pm (\pm 60 minutes).
- Subjects receiving ORMD-0801 bid will receive their doses at approximately 7am (\pm 30 minutes) and before bed at approximately 10pm (\pm 60 minutes), while receiving placebo at approximately 1pm (\pm 60 minutes).
- Subjects receiving ORMD-0801 tid will receive their doses at approximately 7am (\pm 60 minutes), at approximately 1pm (\pm 60 minutes), and before bed at approximately 10pm (\pm 60 minutes).

5.4 Dose Modifications

This study does not include any planned dose modifications. Subjects will be administered study treatment orally at the assigned (randomized) dose level unless discontinuation criteria as defined in Section 4.3 are met.

5.5 Measuring Subject Compliance

5.5.1 Study Treatment Periods 1 and 2

Four doses of placebo (8 capsules) will be dispensed to subjects for Day 1 and Day 2. Compliance will be reviewed during admission on Day 2 to protect the single-blind nature of this treatment.

All doses of study treatment will be administered in the CRU. Oral dosing compliance will be ascertained by inspection of the oral cavity (mouth check) following dosing.

5.6 Drug Accountability

In accordance with current GCP, the Investigational Site will account for all study treatment supplies. Details of receipt, storage, administration, and return or destruction will be recorded in the Investigational Drug accountability record according to the SOP of the Investigational Site. Copies of the Investigational Drug accountability record will be provided to the Sponsor.

Study treatment will only be dispensed to subjects enrolled in this protocol, and only as directed by this protocol. Administration of study treatment will be accurately recorded in each subject's source documents and CRF.

5.7 Concomitant Medications and Supplements

All medications and supplements (other than study treatment) taken by the subject from Visit 2/Day 1 through the Follow-up Visit 3 will be considered "concomitant" medications and supplements. Medications and supplements taken prior to Visit 2 that are no longer being taken at the time of Visit 2/Day 1 will be considered "prior" medications and supplements.

All prior medications and supplements taken within 30 days prior to the first dose of study treatment and concomitant medications and supplements will be recorded in the subject's source documentation and in the CRF.

The use of concomitant medications and supplements should be kept at a minimum, if possible. Any medications and supplements needed for the welfare of a subject and that in the judgment of the Investigator will not pose a significant risk to the subject for continued participation in the study or that will not interfere with the interpretation of the results of this study may be given to the subject. If a subject requires the use of any of the prohibited medications and supplements listed below, the Investigator will contact the Sponsor and the Medical Monitor to discuss the subject's continued participation in the study. In the event of an emergency, subjects will be treated at the discretion of the Investigator according to acceptable community standards of medical care.

The following are prohibited medications:

1. Any Investigational Drug other than ORMD-0801 (or placebo) within 30 days prior to Visit 2/Day 1 through the Follow-Up Visit 3;
2. Any anti-diabetic drugs (except for those allowable by the inclusion criteria) including insulin, GLP-1 analogue, α -glucosidase inhibitors, glinides, and pramlintide;
3. Aprotinin (e.g., Trasylol);
4. Thyroid preparations or thyroxine (except in subjects on stable replacement therapy);
5. Systemic long-acting corticosteroids or other systemic corticosteroids or inhaled corticosteroids (if daily dosage is $> 1,000 \mu\text{g}$ equivalent beclomethasone). Intra-articular and/or topical corticosteroids are not considered systemic.
6. Medications known to modify glucose metabolism or to decrease the ability to recover from hypoglycemia such as oral, parenteral, and inhaled steroids, and immunosuppressive or immunomodulating agents.

If the subject initiates prohibited drug therapy, or if the Investigator determines that use of a prohibited therapy is in the best interest of the patient's health and well-being, the Investigator and sponsor will jointly decide to continue or discontinue the subject.

